### **1.5 Rationale for the protocol design**

The purpose of the trial is to determine if the addition of SABR to ceritinib can prolong the clinical benefit of targeted therapy. This will be an open-label, non-randomized, two arm trial in *ALK* + lung adenocarcinoma. The protocol will also report the safety of treating with SABR and ceritinib, though both are widely used in clinical practice.

Crizotinib is widely used for *ALK* + lung adenocarcinoma. Ceritinib is FDA approved as subsequent therapy for *ALK* + lung adenocarcinoma. As both are excellent options for treatment of *ALK*+ lung cancer, the trial will consist of two cohorts. The first will be for patients who have never been treated with an *ALK* inhibitor, the other will be for patients who have progressed on one *ALK* inhibitor.

### **1.6 Rationale for dose and regimen selection**

The package insert for ceritinib recommends a starting dose of 750 mg daily. There are recommendations for dose adjustments for toxicity and renal/hepatic impairment. This dose has been associated with gastrointestinal toxicities often necessitating a dose reduction. In clinical practice, the starting dose is lower and side effects mitigated by the addition of food with the dose.

In a phase I study of Ceritinib 450 mg or 600 mg with a low fat meal was compared to 750 mg in *ALK*+ non small cell lung cancer. In this ASCEND-8 study, 137 patients were randomized to 750 mg daily with no food, 600 mg daily with food or 450 mg daily with food. The 750 mg dose patients showed similar

STU042015-076, [name], FormA-ResearchProtocol-V6, Mod\_19, 04-09-20 (1)

CONFIDENTIAL

This material is the property of the [UTSW Simmons Cancer Center](#). Do not disclose or use except as authorized in writing by the study sponsor.

steady state pharmacokinetics, while the 600 mg arm shows a 25% higher PK. The incidences of GI related AE's were lowest in the 450 mg arm with no grade 3 or 4 toxicities, while the remaining toxicities were similar. These data were presented in the Journal of Thoracic Oncology in 2017 (s1184, vol.12, No 1S).

## 2.0 Study Objectives

The hypothesis is that delivering SABR to patients with persisting tumors 10 weeks after ceritinib will result in superior overall tumor control, prolong PFS for patients and lengthen the duration of ceritinib activity in patients with *ALK*+ lung adenocarcinoma.

Published experience suggests that median PFS for patients who have previously been treated with crizotinib is less with ceritinib than those who have never been treated with crizotinib (7 months vs 10 months) (Shaw et al, NEJM 2014). As a result patients enrolled on this study will be divided into cohorts on the basis of prior exposure to crizotinib.

The primary endpoint of this study will be Progression-Free Survival (PFS); defined as time from initiation of ceritinib to evidence of disease progression by RECIST 1.1, unacceptable toxicity, withdrawal of consent, or discontinuation of the trial for any other reason.

There may be progression in a specific localized region that is amenable to stereotactic radiation. If all existing lesions that enlarge and any new lesions that develop can still be effectively treated with stereotactic radiation, patients will be evaluated for repeat SABR therapy and ceritinib resumed. This will be at the recommendation of the treating physician according to standard practice. This will be defined as Time to 2nd SABR therapy and will be one of the secondary endpoints.

Similarly, if 3rd round of SABR can be safely provided with subsequent resumption of ceritinib, it will be defined as the Time to 3rd SABR therapy.

### Cohort A (*ALK* inhibitor naive):

**Primary Objective:** To demonstrate the superiority of ceritinib combined with SABR in prolonging median PFS compared to historical control of 10 months

**Primary Endpoint:** Median PFS (as described in section 2.0) for study cohort, expected to be 20 months

**Hypothesis:** The addition of stereotactic radiation in patients with *ALK*+ lung adenocarcinoma receiving ceritinib will enhance efficacy leading to prolongation of time on ceritinib monotherapy.

**Secondary Objectives:** To describe overall survival in study participants  
To describe the time to 2nd and 3rd SABR therapy  
To determine the number of patients with CR, PR or stable disease by RECIST 1.1 criteria at 6 and 12 months

**Secondary Endpoints:** Overall survival  
Time to 2nd SABR treatment, Time to 3rd SABR treatment

PFS at 6 and 12 months from study initiation therapy

**Safety Objectives:** Demonstrate safety of ceritinib followed by SABR.

Safety Endpoints: toxicity and adverse events (CTCAE v.4)

**Hypothesis:** the safety of this combination of targeted therapy and radiation will be as safe as published experience of both these agents.

Cohort B (treated with one prior ALK-inhibitor):

**Primary Objective:** To demonstrate the superiority of ceritinib combined with SABR in prolonging median PFS compared to historical control of 7 months

Primary Endpoint: Median PFS (Time to subsequent systemic therapy) for study cohort, expected to be 14 months.

**Hypothesis:** the addition of stereotactic radiation in patients with ALK+ lung adenocarcinoma receiving ceritinib will enhance efficacy and prolongation of time on ceritinib monotherapy.

**Secondary Objectives:** To describe overall survival in study participants  
To describe the time to 2nd and 3rd SABR therapy  
To determine the number of patients with CR, PR or stable disease by RECIST 1.1 criteria at 6 and 12 months

Secondary Endpoints: Overall survival  
Time to 2nd SABR treatment, Time to 3rd SABR treatment  
PFS at 6 and 12 months from study initiation

**Hypothesis:** The combination of SABR and ceritinib will result in a clinically meaningful overall survival in study participants.

The early application of SABR will be effective in delaying progression which is amenable to SABR but does not require a change in systemic therapy

**Safety Objectives:** Demonstrate safety of ceritinib followed by SABR.

Safety Endpoints: toxicity and adverse events (CTCAE v.4)

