### 2.3 Definition of end of the Study

The study will end when all 33 patients have evidence of disease progression by RECIST1.1, unacceptable toxicity, withdrawal of consent, or discontinuation of the trial for any other reason.

At the completion or discontinuation of study medication, all patients will be seen within 30 days for an end of therapy evaluation. This will include a safety assessment for AE's SAE's. Any unused medication will be returned.

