**Study Design:**

**Purpose:** of this prospective, single-center, two cohort, non-randomized trial is to evaluate the impact of the combination of ceritinib and stereotactic radiation delivered to patients with *ALK*-rearranged adenocarcinoma. The enhanced efficacy of this combination is to be evaluated specifically with regards to prolongation of clinical benefit of ceritinib. We will also evaluate the safety of this combination of targeted therapy and radiation.

For *ALK*-rearranged patients started on ceritinib and treated with SABR to persisting lesions:  
 -PFS compared to published historical results with ceritinib alone PFS=7 month for prior crizotinib treated and 10 month for no previous crizotinib therapy (Shaw et al, NEJM 2014).  
 PFS will be defined as Time to Subsequent Systemic Therapy.

As secondary objectives, we will also report overall survival and time to 2nd and 3rd SABR for each cohort.

	Objective	Endpoint
Primary:	Cohort A: Superiority of ceritinib + SABR median PFS compared to historical control of 10 months (expected to be 20 months)  Cohort B: Superiority of ceritinib + SABR median PFS compared to historical control of 7 months	Cohort A Median PFS defined as time from initiation of ceritinib until disease progression by RECIST 1.1, unacceptable toxicity, withdrawal of consent, or discontinuation of the trial for any other reason including death.  Cohort B: Median PFS defined as time from initiation of ceritinib until disease progression by RECIST 1.1, unacceptable toxicity, withdrawal of consent, or discontinuation of the trial for any other reason including death.
Secondary:	Report Overall survival  Report Time to 2 nd SABR  Report Time to 3 rd SABR  Report proportion of patients CR/PR/stable disease at 6 and 12 months	Overall survival  Time from start of systemic therapy to first day of second course of SABR  Time from start of therapy to first day of third course of SABR  Number of patients with CR/PR/stable disease for 6 and 12 months after initiation
Safety:	Demonstrate safety of ceritinib followed by SABR	Describe toxicity and adverse events (CTCAE v.4) compared to historical controls.

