### *Cohort A (no prior ALK-inhibitor):*

A sample size of 18 patients achieves 80% power to detect the difference between the null hypothesis of median PFS of 10 months and the alternative hypothesis of median PFS of 20 months at two-sided significance level of 0.1. We assume the patient accrual period of 36 months and the follow-up period of 12 months. The assumption that patients are randomized until the end of accrual. The sample size was estimated using SWOG ([https://www.swogstat.org/stat/public/one\\_survival.htm](https://www.swogstat.org/stat/public/one_survival.htm)) sample size calculator.

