## 9.3 Data Analyses Plans

We will use Kaplan-Meier methods to estimate the progression-free survival, time to 2nd and 3rd SABR and overall survival.

Duration of response (defined in 6.1.5) duration will be summarized for patients who responded. Descriptive summary statistics like median, 25% and 75% percentiles will be used.

Toxicities are dichotomized as none versus any, or none and mild versus moderate to severe.

The rates of overall response, toxicity and adverse events as well as their 95% confidence intervals will be estimated using exact binomial method.

We will compare the rates of toxicity and adverse events in this study with those of historical controls by the Fisher's exact test.

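### The safety objective is to demonstrate that the combination is as safe as published experience, but Fisher's test of difference, with no margin, alpha or named control, cannot support that, and two other sections call the aim descriptive

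*Combined protocol and SAP*

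**What the plan says.** Section 2.0, Cohort A, gives the safety hypothesis that "the safety of this combination of targeted therapy and radiation will be as safe as published experience of both these agents". The safety objective for both cohorts there, and in the section 9.1 table, is to "Demonstrate safety of ceritinib followed by SABR". The endpoint column of that table asks for toxicity to be described against historical controls.

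Section 9.3 supplies the method: "We will compare the rates of toxicity and adverse events in this study with those of historical controls by the Fisher's exact test". It states no significance level, sidedness, margin, power or multiplicity rule, and does not say which dataset supplies the safety controls. The preceding sentence plans estimation: the rates of response, toxicity and adverse events "as well as their 95% confidence intervals will be estimated using exact binomial method". The cut-points are also fixed there: "Toxicities are dichotomized as none versus any, or none and mild versus moderate to severe".

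Elsewhere the aim is weaker. The closing text of section 2.0 says that the safety objective is to report the toxicity profile, and section 9.10.2 says that it is to describe toxicities. The as-safe-as hypothesis is printed for Cohort A only.

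**The concern.** Fisher's test can give evidence that the combination is worse than the historical series. It cannot give evidence that it is as safe: failing to reject equality is not support for equality, least of all in a small sample. With an as-safe-as hypothesis, an objective to demonstrate safety, a single test of difference and no margin, the plan offers no valid route from the data to its stated safety conclusion.

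The protocol itself says, in the section 1.3.3 text on ceritinib during stereotactic radiation, that safety data on concurrent use are limited. Section 7.1.2 warns of severe pneumonitis, sometimes fatal. Less common serious events are where a test in 33 patients is weakest and where an unsupported claim of comparable safety would matter most.

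**Working it through.** **1. The plan's own sample size.** The only sizing is for PFS: "A sample size of 18 patients achieves 80% power to detect the difference" in Cohort A (median 10 v 20 months) and 15 patients in Cohort B (7 v 14), at two-sided 0.10, with 36 months' accrual and 12 months' follow-up. For an exponential one-sample test on the log hazard, N = [(1.645/√p0 + 0.842/√p1) / ln 2]², where p = 1 − [exp(−12λ) − exp(−48λ)]/(36λ) and λ = ln 2/median.
- Cohort A: p0 = 0.840, p1 = 0.623, N = 17.04; power at 18 is 81.7%.
- Cohort B: p0 = 0.917, p1 = 0.742, N = 15.11; power at 15 is 79.8%.

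The stated 18 + 15 = 33 is reproduced, and it owes nothing to safety.

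**2. Inputs for the safety comparison.**
- Section 1.3.1.2.1 gives grade 3-4 rates of ALT 21%, AST 11%, diarrhea 7% and lipase 7%.
- Section 7.1.4 gives ALT 15.5%, AST 7.3% and diarrhea 5.9%.
- Assumed, because the plan does not say: two-sided 0.05, and a control size of 114 (response-evaluable patients, section 1.3.1.2.1), 220 (ECG series, section 7.1.4) or 246 (phase I total, section 1.1.2).
- A doubling is used only as a yardstick.

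**3. Chance that a true doubling is significant.** For a published rate r and N controls, take the historical count as N × r, rounded. Find the smallest count x* of 33 with a Fisher p-value below 0.05. Power is then P(Bin(33, 2r) ≥ x*).

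| Event, r → 2r | Controls (events) | x* | Power |
|---|---|---|---|
| Diarrhea, lipase, 7% → 14% | 114 (8) | 7 | 17% |
| Same | 246 (17) | 6 | 31% |
| AST, 11% → 22% | 114 (13) | 9 | 29% |
| Same | 246 (27) | 8 | 44% |
| ALT, 15.5% → 31% | 114 (18) | 11 | 45% |
| Same | 220 (34) | 10 | 60% |
| ALT, 21% → 42% | 114 (24) or 246 (52) | 13 | 68% |

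With the other section 7.1.4 rates and 220 controls, the figures are 35% for AST (7.3%) and 19% for diarrhea (5.9%).

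**4. Sensitivity.** Against 246 controls, a level of 0.10 gives 31%, 44% and 80% at rates of 7%, 11% and 21%. Letting the historical count vary at random, at 0.05, gives 28%, 38% and 69%. In Cohort A alone (18 patients), where the hypothesis is printed, power at 0.05 is 10-24% at 7%, 19% at 11%, 31% at 15.5% and 51% at 21%.

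**5. What a non-significant result leaves open.** Suppose 5/33 (15%) against 17/246 (7%), an observed doubling. Fisher gives p = 0.16, while the exact 95% interval for 5/33 is 5.1% to 31.9%. With 2/33 events (6%, close to the published 7%), the interval is 0.7% to 20.2%, and 20.2/7 = 2.9 times the published rate.

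**6. Could a ceiling rule work at this size?** Take an illustrative ceiling of 2r on the exact 95% upper limit. At r = 7% the ceiling is 14%. The upper limit for 0/33 is 1 − 0.025^(1/33) = 10.6%, and for 1/33 it is 15.8%, so only 0/33 passes. If the true rate is 7%, that has probability 0.93^33 = 9%. At r = 21% the ceiling is 42%; 7/33 passes (38.9%) and 8/33 does not (42.3%), and P(Bin(33, 0.21) ≤ 7) = 61%.

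**The case against.** The strongest reply is that safety is a non-primary, descriptive aim in a 33-patient phase II trial. The closing text of section 2.0 and section 9.10.2 say so, the section 9.1 endpoint uses the verb describe, and section 9.3 already plans exact 95% intervals that would display the uncertainty. That stands in part. The intervals are planned, so Fisher's test is not the only safety analysis, and much of the fix uses what is already there. It does not remove the conflict: sections 2.0 and 9.1 still say demonstrate, the as-safe-as hypothesis is still printed, and no ceiling is given against which to judge the intervals.

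Three stronger readings are tempting, and the documents do not support them.
- A reader might infer that a non-significant p-value will be reported as proof of safety. No section states that rule. The defect is that the plan gives no valid rule for concluding on its hypothesis.
- A reader might infer that any clear worsening would usually be missed. For ALT at 21% a doubling is detected in 68% of trials, and at 15.5% in 45-60%. On the same assumptions, a tripling is detected in 56-72% of trials at 7% and 81-90% at 11%.
- A reader might take the table above as the power of the planned test. Grade 3 or higher is not one of the planned cuts. The published rate for moderate-to-severe toxicity is not given; if it were 25% or more, power for a doubling would exceed 75%. Any-grade nausea (82%) and diarrhea (75%) cannot double at all.

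**Conclusion.** The point holds in this form: the stated analysis cannot support the stated safety hypothesis, and the sections disagree on whether safety is to be demonstrated or described. The mismatch of hypothesis and test is a matter of logic and does not depend on which control is chosen.

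Its size does depend on assumptions. At two-sided 0.05, with 114 to 246 controls and all 33 patients pooled, a true doubling would be non-significant in 69-83% of trials for grade 3-4 events published at 7%, 56-71% at 11%, and 32-55% for ALT at 15.5-21%. The level, the control size and the grade 3-4 cut are assumed because the plan fixes none of them for this comparison. The primary PFS analysis is unaffected.

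**What to change.** 1. In section 2.0 (both cohorts) and the section 9.1 table, restate the safety objective as descriptive, and reword or remove the Cohort A as-safe-as hypothesis, in line with the closing text of section 2.0 and section 9.10.2.
2. In section 9.3, state that a non-significant Fisher result is not evidence of comparable safety. Drop the test, or label it descriptive and name the control dataset and level.
3. Base the safety statement on the exact 95% intervals already planned. Add a grade 3 or higher cut and the section 7.3.2 events of special interest, each shown beside the published rate and its source.
4. Keep as-safe-as wording only for an event whose exact upper limit lies below a ceiling fixed beforehand. Say openly that with 33 patients this is rarely attainable for events near 7%: a 14% ceiling needs 0/33 events.

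The cost is a change of wording in the objectives and analysis plan plus one extra tabulation, with no added patients or procedures. The downside is a less favourable safety claim.

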**Hypothesis:**

The primary objective is to describe the PFS in patients undergoing study therapy. This is defined as evidence of disease progression by RECIST, unacceptable toxicity, withdrawal of consent, or discontinuation of the trial for any other reason.

Additional SABR to enlarging lesions will be permitted while on ceritinib, but no change in systemic therapy will be allowed. Patients who demonstrate oligo progression and have disease amenable to repeat courses of radiation therapy may resume ceritinib at the discretion of the treating oncologist until a change in systemic therapy is indicated.

The secondary objective of the study is to report overall survival and in *ALK*-positive lung adenocarcinoma. We will use Kaplan-Meier methods to estimate the overall survival. The rate of overall response and its 95% confidence interval will be estimated using exact binomial method. Response duration will be summarized for patients who responded. Descriptive summary statistics like median, 25% and 75% percentiles will be used.

The secondary objective is also to describe the time to subsequent SABR in patients undergoing study therapy. Patients will be retreated with SABR if feasible. After the initial SABR to persisting lesions, if new lesions appear or if existing lesions enlarge but are amenable to SABR, patients will remain on study and listed as not having progressed. This time to 2nd and 3rd SABR will be recorded and reported. The secondary endpoint will be recorded as time to 2nd and (if applicable) 3rd SABR therapy.

The safety objective of this study to report the toxicity profile of the combination of ceritinib and SABR therapy. Both are well tolerated and routinely used in non-small cell lung cancer.

## 2.1 Translational and exploratory objectives

Radiation can potentially reverse tumor cell unresponsiveness in patients, even in sites that are have not been radiated. As noted above[17] (and in press), M1 and M2 macrophages play different roles in the tumor metastasis. *ALK* inhibition impacts the immunologic profile and potentially the subsequent development of metastases.

The exploratory objectives of this study would be to determine the impact of *ALK* inhibition and radiation on immune cell such as VEGFR2 expression, CD4/CD8 T-cells, NK cells and macrophages,. Blood will be collected at various time points during the study to determine any association with ceritinib or radiation.

## 2.2 Description of protocol design

This is an, open-label, two-cohort protocol designed to evaluate the activity of targeted therapy and SABR in *ALK*+ lung adenocarcinoma. Study participants will have to be eligible for both radiation and targeted therapy with ceritinib.

### 2.2.1 Treatment phase and duration of treatment

Patients eligible for treatment will receive 450 mg daily of ceritinib as part of a 28 day cycle. The first dose of each cycle will be administered after evaluation at the study center. Patients will remain on study and take ceritinib until there is evidence of disease progression by RECIST 1.1, unacceptable toxicity, withdrawal of consent, or discontinuation of the trial for any other reason. In case of oligoprogression amenable to repeat courses of SABR, the treating oncologist may resume ceritinib if it is indicated per standard clinical practice. Patients must continue to be followed for safety and efficacy assessments as per the schedule of assessments.

After 2 treatment cycles, lesions will be assessed by treating physician per RECIST 1.1. Persisting lesions will be treated with a course of SABR as feasible following at least 10 weeks of ceritinib treatment. Ceritinib will be held 3 days before the start of radiation. Patients will resume ceritinib 3 days

after completion of the SABR. Regular surveillance will follow and any new or enlarging lesions that develop will be assessed for repeat SABR.

### 2.3 Definition of end of the Study

The study will end when all 33 patients have evidence of disease progression by RECIST1.1, unacceptable toxicity, withdrawal of consent, or discontinuation of the trial for any other reason.

At the completion or discontinuation of study medication, all patients will be seen within 30 days for an end of therapy evaluation. This will include a safety assessment for AE's SAE's. Any unused medication will be returned.

### 2.4 Early Termination

Treatment on protocol may be terminated early if the Principal investigator or institution assess that the safety of the enrolled subjects will be compromised by continuation of the trial. The procedure followed will be that of the premature withdrawal patient and any patients on treatment will be seen as soon as possible.

## 3.0 Subject eligibility

### 3.1 Patient population

Subjects for this study will be selected from those with *ALK*+ lung adenocarcinoma. *ALK* analysis by Ventana or Vysis assay is routinely performed on lung adenocarcinoma to determine *ALK* status. Patients who are positive for an *ALK* rearrangement by gene sequencing will also be considered eligible for the study.

Patients will be informed about their potential eligibility status for this trial. None of these patients will be given any therapy or undergo any study related assessments/procedures until they have successfully screened and enrolled on to the therapeutic portion of the study.

Patients enrolled to the therapeutic portion of the study will have histologically proven lung adenocarcinoma with *ALK* abnormality detected by gene sequencing or assay as described above.

